4.5.1.2 Investigational Product Inspection

Each vial selected for dose preparation should be inspected. If there are any defects noted with the investigational product, the investigator and site monitor should be notified immediately. Refer to the Product Complaint section, Section 4.5.1.6, for further instructions.

4.5.1.3 Dose Preparation Steps

The dose of MEDI6012 or placebo for administration must be prepared by the unblinded investigational product manager or other qualified professional using aseptic technique. Only remove from storage the required MEDI6012 or placebo vials and IVBP vials required for subject dosing.

For the IV infused doses (Cohorts 1-3 only), IVBP must be used to precondition the IV bag prior to addition of the MEDI6012 or placebo dose (specific instructions below).

Follow the guidelines of the IV bag manufacturer for maximum number of allowable punctures through the injection port; if needed, use an intermittent adaptor for the dose preparation into the injection port.

Preparation and Administration of MEDI6012 or Placebo for IV Infusion (Cohorts 1-3)

The admixture for 40, 120, and 300 mg IV doses should be prepared in a 50 mL polyolefin 0.9% (w/v) saline IV bag containing IVBP using a single step dilution. The prepared dose will be delivered using a PVC (DEHP-free) IV administration set with a 0.22 or 0.2-µm PES filter. Following completion of infusion, a flush of the IV administration set should be performed by adding up to 30 mL of 0.9% (w/v) saline (or equivalent corresponding to the hold-up volume of the extension set) to the IV bag to obtain the full dose. The dose preparation procedure is as follows in Table 4.5.1.3-1.

Table 4.5.1.3-1 Investigational Product Dose Preparation for 40 mg, 120 mg and 300 mg MEDI6012 or Placebo IV Doses

Step	Instructions
	1. Obtain a 50 mL IV saline bag.
	2. Remove entire volume (ie, 50 mL saline plus the manufacturer's overfill) from the IV bag. Do not discard.
D C40	3. Add 50 mL of saline back into IV bag.
Preparation of 40 mg dose of MEDI6012 or	4. Remove and discard a total volume of 2.4 mL saline from the IV bag.
placebo for IV administration	5. Slowly add 2.0 mL of IVBP. Mix the contents of the IV bag by gentle inversion for 30 seconds.
	6. Slowly add 0.4 mL of MEDI6012 from a reconstituted vial or placebo using a 3.0 mL syringe. Mix the contents of the IV bag by gentle inversion for 30 seconds.
	7. Inspect the IV bag to ensure solution is clear.
	1. Obtain a 50 mL IV saline bag.
	2. Remove entire volume (ie, 50 mL saline plus the manufacturer's overfill) from the IV bag. Do not discard.
D 4: C120	3. Add 50 mL of saline back into IV bag.
Preparation of 120 mg dose of MEDI6012 or	4. Remove and discard a total volume of 3.2 mL saline from the IV bag.
placebo for IV administration	5. Slowly add 2.0 mL of IVBP. Mix the contents of the IV bag by gentle inversion for 30 seconds.
	6. Slowly add 1.2 mL of MEDI6012 from a reconstituted vial or placebo using a 3.0 mL syringe. Mix the contents of the IV bag by gentle inversion for 30 seconds.
	7. Inspect the IV bag to ensure solution is clear.
	1. Obtain a 50 mL IV saline bag.
	2. Remove entire volume (ie, 50 mL saline plus the manufacturer's overfill) from the IV bag. Do not discard.
D 4: C200	3. Add 50 mL of saline back into IV bag.
Preparation of 300 mg dose of MEDI6012 or	4. Remove and discard a total volume of 5.0 mL saline from the IV bag.
placebo for IV administration	5. Slowly add 2.0 mL of IVBP. Mix the contents of the IV bag by gentle inversion for 30 seconds.
	6. Slowly add 3.0 mL of MEDI6012 from a reconstituted vial or placebo using a 3.0 mL syringe. Mix the contents of the IV bag by gentle inversion for 30 seconds.
	7. Inspect the IV bag to ensure solution is clear.

IV = intravenous; IVBP = intravenous bag protectant.

Preparation and Administration of MEDI6012 or Placebo by IV Push (Cohort 4)

For each dose level delivered by IV push, Table 4.5.1.3-2 describes the delivery volume (mL), the required number of vials, and number of required syringes for each dose.

Table 4.5.1.3-2 Investigational Product IV Push Delivery Volume and Vial Usage

Dose (mg)	Total Delive	•	Number o Requi			f 1 mL Syringes equired
	MEDI6012	Placebo	MEDI6012	Placebo	MEDI6012	Placebo
300 (Dose #1)	3.0	3.0	6	1	3	3
150 (Dose #2)	1.5	1.5	3	1	2	2
100 (Dose #3)	1.0	1.0	2	1	1	1

IV = intravenous

MEDI6012 or placebo is pooled in each 1 mL syringe (polycarbonate/ polypropylene) and dosed based on the delivery volume as shown in Table 4.5.1.3-2. Each injection will be administered over 30 seconds and each injection will be followed by a 10 mL normal saline flush.

NOTE: The IVBP is not used in the preparation of IV push doses.

4.5.1.4 Treatment Administration

The first day of investigational product dosing is considered Day 1. On each day of dosing, following an overnight fast for a minimum of 6 hours, investigational product will be administered as soon as is practicable after rising.

Investigational product will be administered via IV infusion over a period of approximately 60 minutes (± 5 minutes) (Cohorts 1-3) or IV push over approximately 1-3 minutes, inclusive of flush (Cohort 4).

4.5.1.5 Monitoring of Dose Administration

Vital signs and ECG assessments will be performed before and after dose administration according to the schedule of procedures.

As with any exogenous protein, allergic reactions to dose administration are possible. Therefore, appropriate drugs and medical equipment to treat acute anaphylactic reactions must be immediately available, and study personnel must be trained to recognize and treat anaphylaxis.

4.5.2 Additional Study Medications

Subjects should continue to take their statin therapy at their regular prescribed dose, and any other medication(s) prescribed for their atherosclerotic CVD. MedImmune will not provide statin or any of these other medications.

4.5.3 Labeling

Labels for the investigational product will be prepared in accordance with Good Manufacturing Practice (GMP) and local regulatory guidelines. The label will fulfill GMP Annex 13 requirements for labeling. Label text will be translated into local languages, as required.

4.5.4 Storage

Investigational product and IV bag protectant are stored at 2°C to 8°C.

4.5.5 Treatment Compliance

Investigational product is administered by study site personnel, who will monitor compliance.

4.5.6 Accountability

The investigator's or site's designated investigational product manager is required to maintain accurate investigational product accountability records. Upon completion of the

study, copies of investigational product accountability records will be returned to MedImmune. At the end of the study or upon request, all unused investigational product will be destroyed at the site as per the site's procedure and local regulation. Investigational product destruction capabilities will be evaluated during study feasibility, and if a site doesn't have the capabilities of destroying the investigational product on site, MedImmune will coordinate the return of the investigational product to a designated depot.

The investigational product manager will provide a copy of the site's written destruction procedure to the unblinded site monitor for review by MedImmune.

4.6 Treatment Assignment and Blinding

4.6.1 Methods for Assigning Treatment Groups

An IXRS will be used for randomization to a treatment group and assignment of blinded investigational product kit numbers. A subject is considered randomized into the study when the investigator notifies the IXRS that the subject meets eligibility criteria and the IXRS provides the assignment of blinded investigational product kit numbers to the subject.

For each cohort, 8 subjects will be randomized in a 6:2 ratio to receive MEDI6012 or placebo. Investigational product must be administered within 24 hours after randomization. If there is a delay in the administration of investigational product such that it will not be administered within the specified timeframe, the medical monitor must be notified immediately.

4.6.2 Methods for Ensuring Blinding

This is a blinded study in which the subjects and investigator and contract research organization personnel are blinded to investigational product, and MedImmune staff involved in the study are unblinded. MEDI6012 and placebo are not identical in appearance. Neither the subject nor any of the investigator staff who are involved in the treatment or clinical evaluation of the subjects will be aware of the treatment received (International Council for Harmonisation [ICH E9]). Since MEDI6012 and placebo are not identical in packaging, investigational product will be handled by an unblinded investigational product manager at the site and will be masked prior to administration through the use of tubing or IV bag covers (Cohorts 1-3) and syringe covers (Cohort 4). An independent investigational product monitor will also be unblinded to perform investigational product accountability. In the event that the treatment allocation for a subject becomes known to the investigator or other study staff involved in the management of study subjects, the sponsor must be notified *immediately*. If the treatment allocation for a subject needs to be known to treat an individual subject for an

AE, the investigator must notify the sponsor *immediately*. The site will maintain a written plan detailing which staff members are blinded/unblinded and the process of investigational product administration used to maintain the blind.

4.6.3 Methods for Unblinding

4.6.3.1 Unblinding in the Event of a Medical Emergency

In the event of a medical emergency, the investigator may unblind an individual subject's investigational product allocation. Instructions for unblinding an individual subject's investigational product allocation are contained in the IXRS manual. In general, unblinding should only occur if management of the medical emergency would be different based on the subject having received investigational product. In the majority of cases, the management of a medical emergency would be the same whether or not investigational product was received by the subject. If this was the case, the investigational product allocation should not be unblinded.

MedImmune retains the right to unblind the treatment allocation for SAEs that are unexpected and are suspected to be causally related to an investigational product and that potentially require expedited reporting to regulatory authorities.

4.7 Restrictions During the Study and Concomitant Treatment(s)

Subjects must refrain from strenuous exercise for approximately 48 hours prior to each study day where blood samples for safety (hematology and serum chemistry) will be collected, from screening through final study assessment.

The investigator must be informed as soon as possible about any medication taken from the time of screening until the end of the clinical phase of the study (final study visit). Any concomitant medication(s), including herbal preparations, taken during the study will be recorded in the eCRF.

4.7.1 Permitted Concomitant Medications

It is anticipated that subjects enrolled to this study and with established atherosclerotic CVD will be managed per current treatment guidelines (eg, AHA/ACCF Secondary Prevention and Risk Reduction Therapy for Patients with Coronary and Other Atherosclerotic Vascular Disease, 2011 and ACC/AHA Blood Cholesterol Guideline, 2013) and may therefore be receiving a range of cardio-protective medications, with the exception of prohibited lipid-lowering therapies. Subjects should adhere to their current regimen from screening through end of the study.

Investigators may prescribe concomitant medications or treatments deemed necessary to provide adequate supportive care except for those medications identified as "excluded" as listed in Section 4.7.2. Specifically, subjects should continue to take their regular prescribed dose of statin and blood pressure medication and receive full supportive care during the study, including transfusions of blood and blood products, and treatment with antibiotics, anti-emetics, anti-diarrheals, and analgesics, and other care as deemed appropriate, and in accordance with their institutional guidelines.

4.7.2 Prohibited Concomitant Medications

Concomitant medications, including over-the-counter medications, herbal supplements, and vitamins that may affect control of lipids (except for statins) are prohibited from screening through the final study visit (see Exclusion Criterion 10 for explanation of washout period and Appendix 5 for a list of therapies requiring wash-out). Subjects must be instructed not to take any medications, including over-the-counter products, without first consulting with the investigator.

Due to their effect on lipids, systemic corticosteroids within 28 days prior to screening and throughout the study are also prohibited, except if needed to treat a generalized allergic reaction, anaphylaxis as defined in Appendix 3, or other serious medical condition. Inhaled, intranasal, topical, ophthalmic, and intra-articular corticosteroids are permitted. Systemic corticosteroid use should first be discussed with and permitted by the medical monitor.

4.8 Statistical Evaluation

4.8.1 General Considerations

[figure not shown]
Data will be provided in listings sorted by cohort, treatment group, and subject number. Tabular summaries will be presented by treatment group with placebo group combined when appropriate. Categorical data will be summarized by the number and percentage of subjects in each category. Continuous variables will be summarized by descriptive statistics, including mean, standard deviation, median, minimum, and maximum. Baseline values will be defined as the last valid assessment prior to the first administration of investigational product. Details of endpoint analyses will be described in the statistical analysis plan (SAP).

Definition of Analysis Population

The As-treated Population includes all subjects who receive at least one dose of study investigational product. Subjects will be analyzed according to the treatment they actually receive.

The PK Population includes all subjects in the As-treated Population who have at least one detectable LCAT serum concentration measurement.

4.8.2 Sample Size and Power Calculations

4.8.3 Safety

4.8.3.1 Analysis of Adverse Events

Safety analysis will be based on the As-treated Population. AE collection begins after the subject signs the informed consent document and lasts until the end of the study. TEAEs and TESAEs will be coded by the most updated version of the Medical Dictionary for Regulatory Activities (MedDRA), and the type, incidence, severity, and relationship to investigational product will be summarized. Specific AEs will be counted once for each subject for calculating percentages. In addition, if the same AE occurs multiple times within a particular subject, the highest severity and level of relationship observed will be reported. All TEAEs and TESAEs will be summarized overall, as well as categorized by MedDRA system organ class and preferred term.

4.8.3.2 Analysis of Clinical Laboratory Parameters

Clinical laboratory safety tests including serum chemistry, hematology, and others will be summarized using descriptive statistics at each time point by treatment group with placebo group combined. Change from baseline to each post baseline time point in these data will also be summarized, where appropriate.

4.8.3.3 Analysis of Vital Signs

Vital sign results will be summarized using descriptive statistics at each time point by treatment group.

4.8.3.4 Analysis of ECGs

ECG parameters will also be assessed and summarized descriptively by treatment group.

As part of the cardiac safety evaluation for MEDI6012, a prospectively defined exposure-response analysis for MEDI6012 concentrations and change from baseline ECG intervals will be performed, using data from this study and the previous single ascending dose study, to thoroughly characterize the QTcF and other ECG intervals. A pre-specified workflow will be described in a separate technical document. Results from the exposure-response analysis will not be reported in the CSR.

4.8.4 Immunogenicity

ADA incidence rate and titer will be tabulated for each treatment group. Samples confirmed positive for ADA will be tested and analyzed for nAb and summarized similarly.

4.8.5 Pharmacokinetics

Non-compartmental analysis will be performed for MEDI6012 treated subjects. Serum MEDI6012 mass and activity concentration-time profiles will be summarized by dose cohort. The PK parameters to be reported include C_{max} , time of maximal concentration (T_{max}), AUC, accumulation ratio, and $t_{1/2}$. Descriptive statistics for PK parameters will be provided.

Additional PK analyses may be conducted as appropriate. If the data allow, population PK analysis will be performed but will not be reported in the CSR.

4.8.6 Pharmacodynamics

The PD parameters of primary interest are the baseline-adjusted HDL-C, HDL-CE, and CE AUC_{0-96hr} following Dose 3 administration (AUC_{0-96hr Dose 3}). AUC will be calculated using the trapezoidal rule. Statistical comparison between treatment groups with placebo group combined will be conducted using analysis of covariance (ANCOVA) by adjusting baseline HDL-C and treatment group. The dose-response profile with regard to HDL-C may be explored using MCP-MOD procedure. Other endpoints including AUC_{0-96hr Dose 1}, AUC_{0-168h Dose 3}, and AUC_{1-22d} (AUC from time 0 on Day 1 through 168 hours after Dose 3) for HDL-C, TC, FC, CE, HDL-CE, HDL-UC, non-HDL-C, non-HDL-CE,

non-HDL-UC, LDL-C (by direct measure), apoA1 and apoB will be analyzed similarly to the primary PD endpoint.

Change and the percent change from baseline at each time point for each of the above lipids, lipoproteins, and apolipoproteins as well as VLDL-C, TG, pre\(\beta\)1-HDL, apoAI, apoAII, apoCIII, and apoE will be analyzed and compared using ANCOVA by adjusting baseline and treatment group with placebo group combined.

For ANCOVA, if the data is not normally distributed, the analyses will be conducted on rank-transformed data.

Descriptive statistics will be provided by treatment group for R_{max} (maximum biomarker response) and $(R)T_{max}$ (time to reach maximum biomarker response) for each of these as well. Details of these analyses will be specified in the SAP.

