This is a Phase 2a randomized, blinded (subject/investigator blinded, MedImmune unblinded), placebo-controlled, dose-escalation study to evaluate the safety, PK/PD, and immunogenicity of repeat doses of MEDI6012 in adult subjects with stable atherosclerotic CVD. At least 32 subjects are planned to be randomized across approximately 10 study sites in the United States of America (USA) to evaluate 4 dose levels (40, 120, 300 mg, and an IV push dosing regimen that includes a loading dose of 300 mg followed by a 150 mg maintenance dose at 48 hours and a 100 mg maintenance dose 7 days later) of MEDI6012. Subjects in Cohorts 1-3 will be administered investigational product weekly via intravenous (IV) infusions. Cohort 4 subjects will be administered investigational product using a loading dose of 300 mg (Dose 1) of MEDI6012, a second dose of 150 mg at 48 hours followed by a maintenance dose of 100 mg 1 week later with all doses given by IV push. For each cohort, 8 subjects are planned for randomization in a 6:2 ratio to receive MEDI6012 or placebo. Investigational product will be administered as a 1-hour IV infusion (Cohorts 1-3) or an IV push (Cohort 4).

Subjects will undergo a screening period of up to 28 days. For subjects requiring a washout of dyslipidemia medication or supplement, a 56 day screening period is allowed. Subjects will be admitted to the study center the evening prior to randomization and first dose administration (Day -1) and prior to third dose administration and remain at the study center for 24-36 hours. In lieu of overnight admission, outpatient arrangements such as a hotel stay near the study center or return to home may alternatively be provided. For dose 2, subjects will be observed as inpatients for at least 8 hours following dosing. For Cohort 4, outpatient arrangements may be provided through Day 4. Subjects will be followed as outpatients through 56 days after the last dose of investigational product (Day 71 visit for Cohorts 1-3, Day 66 visit for Cohort 4). Subjects will be encouraged to maintain a healthy lifestyle, including diet and exercise, during the study period.

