The PD parameters of primary interest are the baseline adjusted AUC from time 0 to 96 hours post dose 3 in HDL-C (AUC_{0-96hr Dose 3}), HDL-CE, and CE. AUC will be calculated using the trapezoidal rule. Statistical comparison between treatment groups with placebo group combined will be conducted using analysis of covariance (ANCOVA) by adjusting baseline HDL-C, HDL-CE, and CE and treatment group. Other endpoints including AUC_{0-96hr Dose 1}, AUC_{0-168hr Dose 2}, AUC from time 0 on Day 1 through 168 hours after Dose 3), AUC_{1-22d}, HDL-C, TC, FC, CE, HDL-CE, HDL-UC, non-HDL-C, non-HDL-CE, non-HDL-UC, LDL C (by direct measure), apoA1, and apoB, will be analyzed similarly to the primary PD endpoint.

Change and the percent change from baseline at each time point for each of the above lipids, lipoproteins, and apolipoproteins as well as VLDL-C, TG, pre β 1-HDL, apoA1, apoAII, apoCIII, and apoE will be analyzed and compared using ANCOVA by adjusting baseline and treatment group with placebo group combined.

For ANCOVA, if the data is not normally distributed, the analyses will be conducted on rank-transformed data.

Descriptive statistics will be provided by treatment group for maximum biomarker response (R_{max}) and time to reach maximum biomarker response (R_{max}) for each of these as well.

ADA incidence rate and titer will be tabulated for each treatment group. Samples confirmed positive for ADA will be tested and analyzed for nAb and summarized similarly.

Non-compartmental analysis will be performed for MEDI6012 treated subjects. Serum MEDI6012 mass and activity concentration-time profiles will be summarized by dose cohort. The PK parameters to be reported include maximum plasma concentration of the drug (C_{max}), time of maximal concentration (T_{max}), AUC, accumulation ratio and terminal half-life ($t_{1/2}$). Descriptive statistics for PK parameters will be provided.

Additional PK analyses may be conducted as appropriate. If the data allow, population PK analysis will be performed but will not be reported within the clinical study report (CSR).

Primary analysis: A primary analysis of the safety, immunogenicity, PK, and PD data will be conducted after the last subject has completed or dropped out prior to the last scheduled visit (Day 71 for Cohorts 1-3 or Day 66 for Cohort 4) and will be reported in the CSR. The long-term follow-up data for ADA positive subjects will be reported as an addendum to the CSR.

TABLE OF CONTENTS

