		3.5.5.1 Vital Signs	
		3.5.5.2 Electrocardiogram	
	3.6	Immunogenicity	
	3.7	Pharmacokinetics	
	3.8	Exploratory Endpoints	
4	INTE	RIM ANALYSIS	
5	REFE	ERENCES	

LIST OF IN-TEXT TABLES

Table 3.2-1	Analysis Populations 9	8
-------------	-------------------------------	---

List of Abbreviations

Abbreviation or Specialized Term	Definition
ACS	acute coronary syndrome
ADA	anti-drug antibody
AE	adverse event
AESI	adverse event of special interest
ANCOVA	analysis of covariance
apoAI	apolipoprotein AI
apoAII	apolipoprotein AII
apoB	apolipoprotein B
apoCIII	apolipoprotein CIII
apoE	apolipoprotein E
ATC	Anatomical Therapeutic Chemical
AUC	area under the concentration curve
AUC _{0-96h}	area under concentration curve from 0 to 96 hours
AUC _{0-168h}	area under concentration curve from 0 to 168 hours
BMI	Body mass index
CAD	coronary artery disease
CE	cholesteryl ester
CHD	coronary heart disease
CL	systemic clearance
C _{max}	observed maximum concentration
CSR	clinical study report
CV	cardiovascular
CVD	cardiovascular disease
DEC	Dose Escalation Committee
ECG	electrocardiogram
HbA1c	glycated hemoglobin
HDL	high-density lipoprotein
HDL-C	high-density lipoprotein-cholesterol
HDL-CE	high-density lipoprotein-cholesteryl ester
HDL-UC	high-density lipoprotein-unesterified cholesterol
HIV	human immunodeficiency virus
IV	intravenous(ly)
IXRS	interactive voice/web response system
LCAT	lecithin-cholesterol acyltransferase
LDL	low-density lipoprotein
·	

Statistical Analysis Plan for Protocol D5780C00005 21Jul2017; Final 2.0

Abbreviation or Specialized Term	Definition
LDL-C	low-density lipoprotein-cholesterol
MedDRA	Medical Dictionary for Regulatory Activities
nAb	neutralizing antibody
PD	pharmacodynamics
РК	pharmacokinetics
rhLCAT	recombinant human lecithin-cholesterol acyltransferase
R _{max}	maximum biomarker response
SAE	serious adverse event
SAP	statistical analysis plan
SPP	Statistical programming plan
t _{1/2}	terminal half-life
ТС	total cholesterol
TEAE	treatment-emergent adverse event
TESAE	treatment-emergent serious adverse event
TG	triglyceride(s)
T _{max}	time of maximal concentration
UC	unesterified cholesterol
ULN	upper limit of normal
VLDL	very low-density lipoprotein
VLDL-C	very low-density lipoprotein-cholesterol

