3.4.2 Analysis of Pharmacodynamic Endpoint(s)

AUC will be calculated using the trapezoidal rule. Statistical comparison with regard to AUC between treatment groups will be conducted using analysis of covariance (ANCOVA) by adjusting baseline values and treatment group comparing each active treatment against placebo. The dose-response profile with regard to HDL-C may be explored using MCP-MOD procedure.

Change and the percent change from baseline at each time point for serum concentration of HDL-C, TC, FC, CE, HDL-CE, HDL-UC, non-HDL-C, non-HDL-CE, non-HDL-UC, LDL-C (by direct measure), TG, VLDL-C, apoA1, pre β 1-HDL, apoAII, apoCIII, apoE, and apoB will be analyzed and compared using ANCOVA by adjusting baseline values and treatment. Descriptive statistics will be provided by treatment group for maximum response (R_{max}) and time to maximum response [(R)T_{max}].

For ANCOVA, if the data is not normally distributed, the analyses will be conducted on rank-transformed data.

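### The covariate for the primary PD ANCOVA is stated three ways; run as Protocol 4.8.6 is written, the model could lose precision, chiefly for CE

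*Protocol*

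**What the plan says.** Three current passages describe the same primary model.

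- **Protocol synopsis, Statistical Analyses:** the comparison is made "using analysis of covariance (ANCOVA) by adjusting baseline HDL-C, HDL-CE, and CE and treatment group".
- **Protocol 4.8.6:** the endpoints are introduced with "The PD parameters of primary interest are the baseline-adjusted HDL-C, HDL-CE, and CE", and the comparison is then made "using analysis of covariance (ANCOVA) by adjusting baseline HDL-C and treatment group". The remaining AUC endpoints, which include TC, LDL-C, apoA1 and apoB, are to be handled in the same way as the primary one.
- **SAP 3.4.2:** the AUC comparison is made "by adjusting baseline values and treatment group comparing each active treatment against placebo".

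The next paragraph of 4.8.6, on change from baseline at each time point, asks only for adjustment for baseline and names no analyte. Protocol 4.8.1 leaves the particulars of the endpoint analyses to the SAP. The SAP carries the page header "21Jul2017; Final 2.0"; Protocol Amendment 1 is dated 16Jul2017. Protocol 4.8.1 and SAP 3.1 define baseline identically, as the last valid value before dosing starts.

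**The concern.** Read literally, 4.8.6 adjusts the HDL-CE and CE AUCs for the baseline of a different analyte and carries that rule over to LDL-C, apoB and the rest. The synopsis can be read as three endpoints matched to three baselines, or as one model containing all three. The SAP phrase does not name the analyte.

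Two things are at stake. The first is that the primary model should be uniquely fixed. Sponsor study staff are unblinded (Protocol 4.6.2), and PD observations from Cohorts 1 and 2 of this study had already fed into the Cohort 4 dose rationale (Protocol 3.2.2). The second is precision. Each comparison sets 6 active subjects against 8 pooled placebo subjects, so the residual variance largely determines the width of the interval. An own-baseline covariate removes variance that another analyte's baseline may leave in. This applies even though the AUC is already baseline-adjusted: if a baseline measured with error is subtracted, the result usually stays correlated with that baseline. Protocol 3.1.3 puts HDL-C assay variability at 12% to 20%; no figure is given for CE.

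**Working it through.** **What can be reproduced.** The public text shows no alpha, power, effect size or SD, so there is no stated power to check. The allocation is "For each cohort, 8 subjects are planned for randomization in a 6:2 ratio to receive MEDI6012 or placebo". Four cohorts give 4 × 8 = 32 subjects: 4 × 6 = 24 active and 4 × 2 = 8 placebo.

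**Degrees of freedom.** One model with four active groups and pooled placebo has 5 group means. With one covariate the residual df are 32 − 5 − 1 = 26. With all three baselines entered together they are 32 − 5 − 3 = 24.

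**Standard error with baseline HDL-C in place of the own baseline.** Let r be the within-group correlation of the baseline-adjusted AUC with its own baseline. Let ρ be the correlation of that baseline with baseline HDL-C. Assume HDL-C predicts the endpoint only through the own baseline. Then

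SE ratio = √[(1 − r²ρ²) / (1 − r²)].

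Example for an analyte unrelated to HDL-C: r = 0.5, ρ = 0 gives √(1/0.75) = 1.155. Example for an analyte close to HDL-C: r = 0.5, ρ = 0.90 gives √(0.7975/0.75) = 1.031.

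**Power.** Assume two-sided alpha of 0.05 and 80% power under own-baseline adjustment. With 26 df this corresponds to a difference of 1.572 residual SDs. The noncentrality is 1.572 / √(1/8 + 1/6) = 2.91, and it is divided by the SE ratio. Power comes from the noncentral t distribution.

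Both r and ρ are assumed. Cells show the SE ratio, with power in brackets.

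| r | ρ = 0 | ρ = 0.3 | ρ = 0.90 | ρ = 0.95 |
|---|---|---|---|---|
| 0 | 1.000 (80.0%) | 1.000 (80.0%) | 1.000 (80.0%) | 1.000 (80.0%) |
| 0.3 | 1.048 (76.2%) | 1.044 (76.5%) | 1.009 (79.3%) | 1.005 (79.6%) |
| 0.5 | 1.155 (68.0%) | 1.142 (69.0%) | 1.031 (77.5%) | 1.016 (78.7%) |
| 0.7 | 1.400 (51.7%) | 1.369 (53.5%) | 1.087 (73.1%) | 1.046 (76.4%) |

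The columns for ρ of 0 and 0.3 stand for an analyte weakly tied to HDL-C, as CE may be. The columns for 0.90 and 0.95 stand for HDL-CE, which Protocol 3.2.4.2 describes as a fraction of HDL-C. Total CE also contains HDL-CE, so its ρ may exceed 0.3. At ρ = 0.6 the ratios are 1.031, 1.102 and 1.271 for r = 0.3, 0.5 and 0.7.

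**All three baselines together.** This model contains the own baseline, so the only certain cost is 2 df. The critical t goes from 2.056 to 2.064, a rise of 0.4%. Power is 79.7% instead of 80% if the extra covariates explain nothing.

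**The case against.** The strongest reply is that the SAP governs and has one natural reading. The protocol defers to it, it is dated five days after Amendment 1, and its single phrase covers every AUC endpoint without carrying over HDL-C. The synopsis lists three endpoints and then the same three baselines, which reads easily as a one-to-one match. On this view the wording in 4.8.6 is leftover shorthand. Most of this stands: own-baseline adjustment is the likeliest intention. It does not remove the conflict, because 4.8.6 names a specific covariate where its next paragraph is generic, and the SAP phrase also fits the list of three. SAP Section 1 mentions a separate programming plan, which may settle the matter but is not among the documents.

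A reader might infer that two of the three primary endpoints lose precision. The documents do not support that. For HDL-CE the two baselines should be so closely related that little is lost, and for CE any loss depends on 4.8.6 being run literally and on correlations that are not given. The correlation of the adjusted AUC with its own baseline could be near zero, for instance if response rises with baseline. Baseline HDL-C could also predict the CE response in its own right, which would shrink the loss.

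A reader might also infer bias, or that the sponsor will pick the covariate after seeing results. Allocation is randomized within each cohort, so the choice of covariate affects precision and reproducibility, not the direction of the estimate. Nothing in the text indicates a choice driven by results; unblinding is only a reason to close the ambiguity. Finally, entering three baselines might look expensive in so small a trial, but the cost in df is negligible.

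**Conclusion.** The inconsistency is confirmed from the text and should be corrected. The precision loss is conditional: it arises only if 4.8.6 is applied as written, and its size cannot be derived from the documents. Under the stated assumptions the SE inflation for an analyte with ρ of 0 to 0.3 runs from nothing at r = 0 to 37-40% at r = 0.7. For HDL-CE with ρ of 0.90 to 0.95 it is about 0.5-9% over r of 0.3 to 0.7. CE is the primary endpoint at possible material risk, together with any secondary lipid weakly related to HDL-C. This is a specification fault of minor to moderate weight, with no systematic bias attached.

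**What to change.** State the same rule in the synopsis, Protocol 4.8.6 and SAP 3.4.2: each AUC endpoint is analysed by ANCOVA with treatment group and that analyte's own baseline as the single covariate (HDL-C for HDL-C, HDL-CE for HDL-CE, CE for CE, and likewise for the other lipids and apolipoproteins). Keep the definition of baseline already in Protocol 4.8.1 and SAP 3.1, so that no second definition is created. The cost is one sentence in three places across two documents. All the baselines are already collected, and no sampling or sample size changes.
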